1.0 Objectives

1.1 Study Objectives

The aim of this study to evaluate and examine, whether use of Hybrid Argon Plasma Coagulation (APC) as adjunct to endoscopic mucosal resection (EMR), will reduce the risk of residual or recurrent neoplasia at 6 months. Hybrid APC is an existing FDA approved device for ablation of abnormal tissue anywhere in GI tract. We hypothesis that with Hybrid APC assisted EMR there will be a decrease in recurrence rate after 6 months and it would be more effective compare to the standard EMR procedure.

1.2 Primary Study Endpoints

Measure Recurrent rate and efficacy of Hybrid APC assisted EMR. Assess rate of local recurrent or residual neoplasia at the EMR scar using optical and histologic classification at 6 months.

1.3 Secondary Study Endpoints

Evaluate rate of post-polypectomy bleeding and post-polypectomy syndrome and compare it to standard procedure.

2.0 Background

2.1 Scientific Background and Gaps

Colon Cancer is a major disease that effecting more than 1 million people per year globally. Adenomatous polyps have been identified as the main precursor in lesions leading to colorectal cancer.¹ Colon cancer screening the best way to detect and remove large, often asymptomatic polyps. Early detection and resection of these colorectal polyps can prevent the development of colon cancer. Endoscopic polypectomy introduced in 1970's, is an effective technique to prevent of colorectal cancer, as demonstrated in National Polyps Study. Endoscipc mucosal resection (EMR) is a technique used for resection of medium to large colon polyps. In this technique, fluid is injected into the submucosal creating a cushion between the mucosa and the muscularis propria. An electrocautery snare is then deployed to resect the polyp in a single (en-bloc) or multiple (piecemeal) pieces. Most of polyps > 2cm are resected in piecemeal way. Although EMR is now considered standard of care with successful rate resection of 85 % and low risk of complication (3-10% bleeding and 1% perforation), this technique has inherent deficiencies, especially piecemeal EMR. This is particularly important if the polyp contains cancer. Resection of scarred polyps using this technique is particularly challenging due to the non-lifting of the polyp. Recurrence rates following piecemeal EMR can be as high as 20%.^{1,2} Endoscopic submucosal dissection (ESD) is an alternative approach that aims to remove non-pedunculated precancerous or cancerous lesions over 20 mm in one piece (en-bloc resection rate of 89.95% and lesion recurrence rate of 0.7%). However, due to its technical complexity and high complication risk (mainly bleeding and perforation, with complication rates approximately 8%), it is not the current standard of care and only performed by experts in the technique.¹ Hybrid Argon plasma coagulation (APC) is a new technique in which the endoscopist reinjects the submucosal with fluid to create a cushion (normal saline/ diluted adrenaline and /or sodium hyaluronate solution) to protect the muscle layer and is then ablated using spray argon coagulation to treat any microscopic residual disease that is the seed for local recurrence .³ Previous studies have shown that this technique is a safe and easily applicable technique to complete resection for recurrent polyps after first EMR.

In this present time there is no study to evaluate the safety and recurrence rate of the Hybrid-APC assisted EMR for large colon polyps at their initial resection attempt

2.2 Previous Data

In 2012 Tsiamoulos et.al. in a single-center, retrospective case series report their experience in regards to endoscopic mucosal ablation (EMA) technique that can be used to complement the eradication of recurrent fibrotic colon polyps. In this study, of consecutive patients referred for endoscopic excision of recurrent benign colon polyps with severe submucosal fibrosis, fourteen patients (mean age 73 years; 9 men, 5 women) with 15 recurrent colon adenomas (mean polyp size 30 mm, 9 proximal/6 distal) were included. EMA with a mean APC power setting of 55 W was applied. Complete polyp eradication was achieved in 9 of 11 patients (82%) at first or second completed follow-up. One patient needed laparoscopic colectomy because of cancer, and 1 underwent transanal endoscopic microsurgery for benign massive recurrence. The other 3 patients with small, easily treatable recurrence (≤ 3 mm) were followed by 1-year-surveillance. No perforations and no postpolypectomy syndrome were reported. They concluded that EMA appears to be a safe and easily applicable technique to assist the complete eradication of recurrent fibrotic colon polyps.³

A systematic review and meta-analysis by Arezzo et.al in 2016 compares the safety and efficacy of endoscopic submucosal dissection (ESD) and endoscopic mucosal resection (EMR) in the treatment of flat and sessile colorectal lesions >20 mm. They reviewed the literature published between January 2000 and March 2014. Pooled estimates of the proportion of patients with en bloc, R0 resection, complications, recurrence, and need for further treatment were compared. A total of 11 studies and 4678 patients were included. The en bloc resection rate was 89.9% for ESD vs 34.9% for EMR patients (RR 1.93 $p<0.001$). The R0 resection rate was 79.6% for ESD vs 36.2% for EMR patients (RR 2.01 $p<0.001$). The rate of perforation was 4.9% for the ESD group and 0.9% for EMR (RR 3.19, $p<0.001$), while the rate of bleeding was 1.9% for ESD and 2.9% for EMR (RR 0.68, $p=0.070$). Therefore, the overall need for further surgery, including surgery for oncologic reasons and surgery for complications, was 7.8% for ESD and 3.0% for EMR (RR 2.40, $p<0.001$). They concluded that ESD achieves a higher rate of en bloc and R0 resection compared to EMR, at the cost of a higher risk of complications.⁴

Manner et.al in 2015 performed a prospective study, which evaluating the efficacy and safety of the new technique of Hybrid-APC which combines submucosal injection with APC in patients with dysplastic Barrett's esophagus. In this study Patients who had a residual Barrett's Esophagus (BE) segment of at least 1 cm after endoscopic resection of early Barrett's neoplasia underwent thermal ablation of BE by Hybrid-APC. Prior to thermal ablation, submucosal injection of sodium chloride 0.9% was carried out using a flexible water-jet probe. Surveillance upper GI endoscopy was carried out 3 months after macroscopically complete ablation including biopsies from the neo-Z-line and the former BE segment, and recording of stricture formation. Total of 60 patients were included in the study [55 pt male (92%); mean age 62 ± 9 years, range 42-79]. Ten patients were excluded from the study. In the remaining 50 pt., Hybrid-APC ablation and surveillance endoscopy at 3 months were carried out. Forty-eight out of 50 pt. achieved macroscopically complete remission after a median of 3.5 APC sessions]. Freedom from BE was histopathologically observed in 39/50 patients (78%). There was one treatment-related stricture (2%). Minor adverse events of Hybrid-APC were observed in 11 patients (22%). It concluded that Hybrid-APC was effective and safe for BE ablation in a tertiary referral center. The rate of stricture formation was only 2%.⁵

2.3 Study Rationale

EMR has a recurrence rate of up to 20% in large ≥ 20 mm lesions with a relatively low risk profile. ESD has a low 1-4% recurrence rate but higher risk profile. We are assessing if adjuvant hybrid APC with EMR drop the recurrence rate near ESD levels while maintaining the safety profile of EMR.

3.0 Inclusion and Exclusion Criteria

3.1 Inclusion Criteria

- Adult patient aged ≥ 18 and ≤ 89 of any gender, ethnicity and race referred to endoscopy for resection of large colon polyps
- Patients with a ≥ 20 mm colon non-pedunculated polyp
- Ability to give written informed consent

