3.2 Exclusion Criteria

- Patients with known (biopsy proven) invasive carcinoma in a potential study polyp
- Pedunculated polyps (as defined by Paris Classification type Ip or Isp)
- Patients with ulcerated depressed lesions (as defined by Paris Classification type III)
- Patients with inflammatory bowel disease
- Patients who are receiving an emergency colonoscopy
- Poor general health (ASA class >3)
- Patients with coagulopathy with an elevated INR ≥ 1.5 , or platelets <50
- Poor bowel preparation
- Target sign or perforation during initial EMR
- Need for ESD for complete resection prior to APC
- Pregnancy and breast feeding

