4.0 Recruitment Methods

4.1 Identification of subjects

We will recruit patients presenting with a known ≥ 20 mm polyp prior colonoscopy and referred for resection of this polyp to Hershey Medical Center.

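### Should the plan restrict entry to first resection attempts, or report recurrence by prior attempt, because the background places the evidence gap there?

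*Combined protocol and SAP*

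**What the plan says.** Section 2.1 (Scientific Background and Gaps) makes two statements about earlier evidence. On polyps already treated once: "Previous studies have shown that this technique is a safe and easily applicable technique to complete resection for recurrent polyps after first EMR". On what is still missing: no study has looked at the safety and "recurrence rate of the Hybrid-APC assisted EMR for large colon polyps at their initial resection attempt".

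The sections that define the study are worded more widely. The aim in Section 1.1 is whether Hybrid APC added to EMR "will reduce the risk of residual or recurrent neoplasia at 6 months", without reference to earlier attempts. Section 2.3 states the comparator in the same terms: "EMR has a recurrence rate of up to 20% in large ≥ 20 mm lesions". Section 3.1 takes adults "referred to endoscopy for resection of large colon polyps" with a non-pedunculated polyp of at least 20 mm, and Section 4.1 recruits patients with a known polyp of that size "referred for resection of this polyp to Hershey Medical Center". Two exclusions in Section 3.2 come close to the subject: "Target sign or perforation during initial EMR" and "Need for ESD for complete resection prior to APC".

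Section 8.3 defines the primary endpoint as a proportion of patients, gives it exact 95% limits, and declares success if the upper limit is below 15%. Its descriptive summaries are introduced as examples, and prior attempt is not among them.

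**The concern.** By the plan's own account, what is new is the first attempt, because the technique had already been studied in recurrent polyps. A patient whose polyp was partly removed elsewhere nevertheless meets every inclusion criterion. The exclusions do not clearly remove such a patient. The one on target sign or perforation reads as an event in the study's own EMR step before ablation, and the one on ESD would catch only some scarred polyps. Section 2.1 also says that scarred polyps are especially hard to resect because they do not lift, so prior attempt is a plausible prognostic factor.

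If such polyps enter and recur more often than the 5% assumed in Section 8.2, the pooled rate would not answer the first-attempt question. The chance of meeting the success rule would fall. The estimate meant to inform a larger study would describe a mixture that readers could not see.

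**Working it through.** **1. Do the defining sections conflict?** Set side by side:

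| Place | Population described |
|---|---|
| 1.1 aim | EMR with Hybrid APC; no limit by attempt |
| 2.3 rationale | lesions of 20 mm or more; no limit |
| 3.1, 3.2 eligibility | non-pedunculated, 20 mm or more; no limit |
| 4.1, 4.2, 4.4 recruitment and screening | known or present polyp of 20 mm or more; no limit |
| 7.1 design | non-pedunculated, 20 mm or more; no limit |
| 8.3 comparator | 15–20% for EMR alone; no limit |
| 2.1 literature gap | initial attempt |

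Only the literature remark is narrower, and it sets no population.

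**2. The plan's power figure.** Inputs from Section 8.2: n = 40, null 15%, alternative 5%, one-sided, power 60%. Alpha is not stated; take 0.05. The normal approximation gives Φ[(0.10 − 1.645·√(0.15·0.85/40)) / √(0.05·0.95/40)] = Φ[(0.10 − 0.0929)/0.0345] = 58%, close to the stated 60%.

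**3. The exact rule.** Clopper–Pearson upper limits for n = 40:

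- Two-sided 95%: 13.2% with 1 event, 16.9% with 2. Success needs at most 1 event.
- One-sided 95%: 14.9% with 2 events, 18.3% with 3. Success needs at most 2 events.

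At a true 5%, the chance of success is 39.9% (at most 1) or 67.7% (at most 2). The distance between these two comes from how the limit is read and has nothing to do with prior attempts.

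**4. Loss of power under assumed mixtures.** The documents give neither the share nor the recurrence rate of previously attempted polyps, so both are assumptions here. Let k of 40 patients have such a polyp, recurring at p₂, and the rest recur at 5%. The total is Bin(40−k, 0.05) + Bin(k, p₂).

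| k | p₂ | P(at most 1) | P(at most 2) |
|---|---|---|---|
| 4, 8 or 12 | 5% | 39.9% | 67.7% |
| 4 | 10% | 34.6% | 62.1% |
| 8 | 10% | 29.8% | 56.6% |
| 12 | 10% | 25.6% | 51.3% |
| 4 | 18% | 26.9% | 53.3% |
| 8 | 18% | 17.6% | 40.1% |
| 12 | 18% | 11.2% | 29.1% |

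The fall runs from nothing to large, and the assumptions alone decide which.

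**5. False success.** At a uniform 15%: P(at most 1) = 1.2% and P(at most 2) = 4.9%. Now suppose the 15% describes all comers, of whom 20% are prior attempts recurring at 25% (assumed). First attempts then recur at (0.15 − 0.20·0.25)/0.80 = 12.5%.

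- *Enrol the same mix, ineffective add-on.* The total is Bin(32, 0.125) + Bin(8, 0.25). P(0) = 0.875³²·0.75⁸ = 0.01394·0.1001 = 0.001396. P(at most 1) = 0.001396·(1 + 32/7 + 8/3) = 1.1%. The two-event term adds 0.001396·(496/49 + 28/9 + (32/7)(8/3)) = 3.5%, so P(at most 2) = 4.7%.
- *Exclude prior attempts but keep the 15% benchmark.* The total is Bin(40, 0.125). P(at most 1) = 3.2% and P(at most 2) = 10.8%.

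Under these assumptions the written population keeps the error rate at or below its nominal size, and the restriction more than doubles it.

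**6. Can prior attempt be identified?** Appendix 1 screens from medical records and earlier reports and includes a polyp eligibility check during the colonoscopy. Sections 7.1 and 7.2 collect polyp characteristics and procedure details. The data form itself is not in the documents.

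**The case for a change.** The strongest case for a change is that a minimal one is nearly free: one yes/no field and one descriptive line, with sample size, eligibility and primary analysis untouched. The plan supplies its own reason to expect a difference, since scarred polyps lift poorly, and it intends to use the interval when deciding on a larger trial. Under the 18% scenario the loss of power is substantial.

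Part of this stands. The scope is unstated, no criterion excludes previously attempted polyps as such, and a reader of the results would want to know how many there were. The rest is weaker. The 18% scenario is an assumption. The number exposed may be small: Section 7.2 relies on submucosal injection to lift the polyp, Section 2.1 says scarred polyps lift poorly, and the ESD exclusion removes some of those that remain. The list of summaries is open, so a count by prior attempt already fits the plan. A first-attempt subgroup would be imprecise: with 1 recurrence its two-sided upper limit is 14.5% for 36 patients, 16.2% for 32 and 18.3% for 28, against 13.2% for 40. It would have no bearing on the success rule.

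**Conclusion.** The concern describes the text correctly but does not call for a change. The plan studies large non-pedunculated polyps referred for EMR, and its defining sections agree with each other and with a comparator stated equally broadly. Followed as written, it yields a valid pooled proportion, and pooling does not inflate false success (1.1% or 4.7% in the illustrative mix, against 1.2% or 4.9%). The possible loss of power runs from zero to a fall from 39.9% to 11.2%, or from 67.7% to 29.1%, over the assumed range; nothing in the documents places the trial within it. Restricting entry would be a trade-off that could weaken the benchmark comparison. A descriptive split would alter neither the primary result nor the success rule.

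This rests on reading the literature remark in Section 2.1 as background, and on the 15–20% rate being as unrestricted as it is worded; the cited sources cannot be checked here. When the results are written up, analysts can reasonably state how many patients had an earlier attempt at the study polyp.

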3.2 Exclusion Criteria

- Patients with known (biopsy proven) invasive carcinoma in a potential study polyp
- Pedunculated polyps (as defined by Paris Classification type Ip or Isp)
- Patients with ulcerated depressed lesions (as defined by Paris Classification type III)
- Patients with inflammatory bowel disease
- Patients who are receiving an emergency colonoscopy
- Poor general health (ASA class >3)
- Patients with coagulopathy with an elevated INR ≥ 1.5 , or platelets <50
- Poor bowel preparation
- Target sign or perforation during initial EMR
- Need for ESD for complete resection prior to APC
- Pregnancy and breast feeding

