3.3.2 Follow-up for withdrawn subjects

Patients will be informed that participation in this study is voluntary and that they do not have to participate in this research. If patients choose to participate, they have the right to stop any time. If a patient decides not to take part in the research or decides to stop taking part in the research at later date, there will be no penalty or loss benefits to which he/she is entitled. The PI of this study has the right to remove patients from the study without their permission. If the investigator determines that the subject does not fulfill the criteria to be in the study, or the subject's condition becomes worse, he may remove the subject from the study.

Information obtained prior to withdrawal may continue to be used if is necessary for the soundness of the overall research. Furthermore, records of the care that we provided will be retained as long as the law requires.

As this is a single point of care investigation, the process of withdrawal may occur between the time of consent and the administration of sedative. Withdrawal may occur either with a written or vocalized desire to retract one's consent.

If a subject is removed from the study prior to completion, the reason for doing so and the date the subject is discontinued will be documented.

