5.0 Consent Process and Documentation

5.1 Consent Process

5.1.1 Obtaining Informed Consent

5.1.1.1 Timing and Location of Consent

Consent and basic demographics will be garnered by the PI, one of the co-investigators or research associate prior to bringing the patient into the endoscopy suite, discussions about the research and obtaining informed consent will occur in curtained endoscopy pre-procedure room. Patients will be given adequate time to review consent form and consult with family if they wish. Patients are not sedated at the time of consent.

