8.3 Statistical methods

The statistical plan for this study was designed with the assistance of [name] with Penn State Public Health Sciences. The primary end point is the rate (proportion of patients) of local recurrent or residual neoplasia at 6 months for the Hybrid Argon Plasma Coagulation (APC) assisted EMR. Estimate of this recurrent rate will provided with 95% exact binomial confidence limits, which will then be compared to the historical rate of 15-20% recurrent rate for EMR alone. Statistical significance will be declared if the upper limit is smaller than 15%. Even when significance is not reached, the confidence interval provides the plausible range of the local recurrent rate of the APC assisted EMR and helps to decide if a future study with a larger sample size is warranted.

Summary statistics such as percentage of male/female patients, percentage of polyps within the different location of colon, mean diameter of polyps, percentage rate of neoplasia recurrence after 6 months, the percentage of each type of Polyps (Ip, Ila, I Ib, I Ic, etc), and Percentage of successful resection will also be provided. SPSS 22 statistical software shall be used to perform statistical analysis.

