10.2 Data that are reviewed

All adverse events will be documented and entered into the Redcap® data management system for centralized data storage and documentation. The following information will be entered: adverse event type, onset/resolution date and time, intensity/severity, action taken, and outcome. All deaths on the study, not related to progression of underlying disease will be reported to the IRB immediately. All unanticipated AE's related or possibly related to study will be reported by PI to the IRB according to HSPO policies and procedures.

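### Exclusions that can be met after EMR has started take unfavourable resections out of the success percentage and EMR perforations out of any reported rate; the bleeding and syndrome comparison also lacks an interval and a reference (minor)

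*Combined protocol and SAP*

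**What the plan says.** Consent (5.1.1.1) is obtained "prior to bringing the patient into the endoscopy suite". Two of the exclusions in 3.2 concern the resection itself: "Target sign or perforation during initial EMR" and "Need for ESD for complete resection prior to APC".

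Among the summary statistics, 8.3 states: "Percentage of successful resection will also be provided". It gives no definition of success and no denominator, and the documents define no analysis set.

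Section 3.3.2 lets the investigator remove a subject who does not meet the criteria, permits continued use of information gathered before withdrawal where the research needs it, and requires that "the reason for doing so and the date the subject is discontinued will be documented". It also remarks that "the process of withdrawal may occur between the time of consent and the administration of sedative". Section 10.2 adds: "All adverse events will be documented and entered into the Redcap". None of these says whether a patient excluded mid-procedure counts in a reported rate.

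For context, 2.1 describes EMR as having a "successful rate resection of 85 % and low risk of complication (3-10% bleeding and 1% perforation"). Section 2.2 cites a second EMR bleeding rate, 2.9%.

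Section 1.3 makes post-polypectomy bleeding and post-polypectomy syndrome the secondary endpoints, to be compared with the standard procedure. The study has one arm (7.1). Section 8.3 specifies exact 95% limits and a historical rate for recurrence only.

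**The concern.** An exclusion triggered by how the resection goes is an exclusion on outcome. A patient who consents, starts EMR and then needs ESD has not had the lesion completed by EMR. If that patient leaves the study, the success percentage is computed among resections that went well enough to proceed to APC. Likewise, a perforation during EMR removes the patient, so the event can be on file and still be absent from any rate over the remaining patients.

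At stake is how the pilot's descriptive results read. A success percentage conditioned in this way describes a favourable subset of EMRs, and nothing in the planned output would tell the reader so.

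The secondary endpoints raise a smaller, separate issue. A comparison is promised without a control arm, an interval or a chosen reference rate. The cited EMR bleeding figures run from 2.9% to 10%, so the reading can depend on a figure picked after the data are seen. The documents cite no EMR rate for the syndrome.

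**Working it through.** The plan gives no figure of its own on this point to reproduce. All intervals below are exact (Clopper-Pearson), two-sided 95%.

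**1. When each exclusion can be met**
- Consent: before the endoscopy suite (5.1.1.1).
- Polyp eligibility and the decision to include: during colonoscopy, listed ahead of EMR with APC (Appendix 1).
- Target sign or perforation during the initial EMR (3.2): only after EMR starts.
- Need for ESD before APC (3.2): on inspection or after EMR starts. Only conversions after EMR starts matter here.

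**2. Direction and possible size for successful resection**

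Let *s* be true success over all EMRs started and *f* the share of non-successes removed under 3.2. Then reported success = *s* / (1 − (1 − *s*)*f*).

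Assume *s* = 0.85, borrowed from 2.1. The documents do not give *f*, so a range is shown:

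| *f* | Calculation | Reported success |
|---|---|---|
| 0 | 0.85/1 | 85.0% |
| 0.25 | 0.85/0.9625 | 88.3% |
| 0.50 | 0.85/0.925 | 91.9% |
| 1 | 0.85/0.85 | 100% |

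The perforation exclusion alone does not push success upward. If 1% perforate and all of those were completely resected, removing them gives (0.85 − 0.01)/0.99 = 84.8%, a fall of 0.2 points. The upward tendency therefore comes from ESD conversions after EMR has started.

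In counts, assuming 40 APC-treated patients and treating conversions as not completed by EMR:

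| APC-treated successes | Conversions added back | Success | Exact lower limit |
|---|---|---|---|
| 40 of 40 | 0 | 100% | 91.2% |
| 40 of 40 | 1 | 40/41 = 97.6% | 87.1% |
| 40 of 40 | 2 | 40/42 = 95.2% | 83.8% |
| 39 of 40 | 0 | 97.5% | 86.8% |
| 39 of 40 | 1 | 39/41 = 95.1% | 83.5% |

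**3. Perforation during EMR**

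At the cited 1%, the chance of at least one in 40 EMR starts is 1 − 0.99^40 = 0.331, or 33%. Among patients who go on to APC under 3.2 the count is zero by construction.

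**4. Bleeding, n = 40, against the two ends of the cited EMR range**

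| Bleeds | Exact 95% limits | Excludes 2.9%? | Excludes 10%? |
|---|---|---|---|
| 0 | 0 to 8.8% | no | yes |
| 1 | 0.06 to 13.2% | no | no |
| 4 | 2.8 to 23.7% | no | no |
| 5 | 4.2 to 26.8% | yes | no |
| 8 | 9.1 to 35.6% | yes | no |
| 9 | 10.8 to 38.5% | yes | yes |

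So 0 bleeds, and 5 to 8 bleeds, read differently at the two ends of the range. The binomial probability of 5 to 8 bleeds is 36% if the true rate is 10% and 0.7% if it is 3%. The probability of 0 bleeds is 1.5% and 30% respectively.

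**The case against.** The strongest reply is that this touches little that the plan sets out to conclude, and much of it stands.

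- **Timing of the ESD exclusion.** Appendix 1 places the inclusion decision ahead of EMR, so the need for ESD may be recognised before resection begins. That stands. Because the upward tendency in success depends on this exclusion, its size depends on how often the need emerges only after EMR has started, and the documents do not say.
- **Comparison with 85%.** A reader might infer that the trial will use the conditioned percentage to claim better success than EMR. The documents do not support that. The percentage is a summary statistic with no test or benchmark, and the 85% is background for medium to large polyps with success undefined, whereas this trial takes polyps of 20 mm or more.
- **Lost data.** A reader might infer from the consent-to-sedation remark in 3.3.2 that patients excluded later fall outside the plan. That is too strong. The same section allows stopping at any time and removal for unmet criteria, requires the reason to be documented, and permits use of earlier data. Adverse events are also recorded (10.2). What is missing is a place for these patients in a denominator.
- **Intraprocedural complications.** No such rate is listed in 1.2, 1.3 or 8.3. The point applies only if one is reported. Perforations arising from APC or later would still be counted.
- **Bleeding.** This is a pilot with no significance rule for bleeding, and a 30-day window is given in Appendix 2. That is correct. The excludes/does-not-exclude reading above is only a way to show how much the choice of reference matters.

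One part of the reply does not stand: recording an event does not settle whether it is counted, and 1.3 does promise a comparison.

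**Conclusion.** The point holds as a minor one, limited to secondary and descriptive outputs. Applied as written, 3.2 removes some consented patients because of what happened during EMR. Successful resection then omits conversions to ESD after EMR has started and tends upward, and any reported rate of perforation during EMR is zero by construction.

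The direction follows from the text; the size does not. The 88.3% to 100% range rests on an assumed true success of 85% and arbitrary excluded shares, and its top end needs every non-success to be excluded. The count examples assume 40 APC-treated patients whatever the number of EMRs started.

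The primary recurrence endpoint, its decision rule and the sample size are not affected by this point. Recurrence after APC-assisted EMR is properly assessed in patients who received APC.

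For bleeding and syndrome, the gap is a promised comparison without an interval or a named reference. A reader might infer that the plan intends to conclude that EMR's safety profile is maintained. That phrase belongs to the rationale in 2.3 and is not a planned conclusion.

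**What to change.** In 8.3:
- Use all consented patients in whom EMR was started as the denominator for successful resection and for any intraprocedural complication reported, including perforation and ESD conversion.
- Report the number of mid-procedure exclusions and the reason for each.
- Keep APC-treated patients as the denominator for recurrence and for post-APC bleeding and syndrome.

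In 1.3 and 8.3:
- Report bleeding and syndrome as n/N with exact 95% intervals.
- Show bleeding descriptively beside the full cited EMR range of 2.9-10%, fixed in advance.
- Report syndrome without a comparison unless a reference rate is cited.

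The cost is wording and a count from records that 3.3.2 and 10.2 already require. The exclusion criteria stay as they are, and no procedure, visit or patient is added. The downside is a possibly lower success percentage and a more modest safety statement.
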